## 2. STUDY DESIGN

### 2.1. General Design

This is a multicenter, randomized, proof-of-concept, double-blind, placebo-controlled, parallel-group study, including an open-label period, evaluating the efficacy and safety of 1 subcutaneous (sc) dose regimen of fremanezumab in adult patients with PTH. The study will consist of a screening visit, a baseline period, a double-blind treatment period lasting approximately 12 weeks, and an open-label period lasting approximately 12 weeks.

The total duration of patient participation in the study is planned to be approximately 28 weeks.

Patients will complete a screening visit (visit 1) after providing informed consent, and eligible patients will enter a baseline period lasting approximately 4 weeks (28+3 days), during which time they will enter their baseline PTH information into a daily electronic headache diary (e-diary). Patients meeting eligibility requirements will be randomly assigned to 1 of 2 treatment groups with fremanezumab or placebo in a 1:1 ratio. Treatment assignment will take place with stratification based on the duration of the patient's history of PTH (<12 months and  $\geq$ 12 months duration).

Screening results will be reviewed for eligibility, additional baseline assessments will be administered, and the first treatment administration will occur at visit 2. Patients will return to the study center approximately every 4 weeks (visit 3 and visit 4) for a continuation of the blinded treatment administered subcutaneously (sc); for safety and efficacy assessments; and for blood and urine sampling for pharmacokinetics, immunogenicity, and biomarker analysis. At visit 5, all patients will proceed directly to an open-label treatment phase, with fremanezumab administered sc. Patients will then return to the study center approximately every 4 weeks (visits 6 and 7) for continued open-label treatment and safety tolerability and efficacy assessments. Final study assessments will be performed on visit 8, at the end of treatment or early termination visit, approximately 24 weeks after first administration of the IMP.

A database lock from the double-blind period will occur following the completion of visit 5 by the last patient. Unblinding will occur after the database lock from the double-blind period.

[figure not shown]
Patients who complete all scheduled visits will have procedures and assessments performed at visit 8. Patients who withdraw from the study before completing either the double-blind or the open-label treatment phases will have visit 8 procedures and assessments performed at their final visit. For all patients in the study, the end-of-treatment visit (visit 8) is defined as the final visit of the study and the conclusion of all study activities for the patient; patients will not receive any further treatments with IMP and will be treated according to guidelines and treating physicians' discretion.

In the open-label period patients will receive 675 mg of fremanezumab administered as 3 sc injections (225 mg/1.5 mL each) at visit 5 (week 12), visit 6 (week 16), and visit 7 (week 20).

The end of study is defined as the last safety visit. However, a final database lock will occur following the end-of-treatment visit (visit 8) of the last patient for analysis of the study data.

The study schematic diagram is presented in Figure 1. Study procedures and assessments with their timing are summarized in Table 1 of the study protocol.

**Figure 1: Overall Study Schematic Diagram**

PBO=placebo; SC=subcutaneous; V=visit.

## 2.2. Randomization and Blinding

Patients meeting eligibility requirements will be randomized into one of the following treatment groups:

1. **Arm A:** Fremanezumab 675-mg sc treatment group

Patients randomized to fremanezumab will receive 675 mg of fremanezumab administered as 3 sc injections (225 mg/1.5 mL each) at visit 2 (randomization), visit 3 (week 4), and visit 4 (week 8).

2. **Arm B:** Placebo treatment group

Patients randomized to placebo will receive placebo administered as 3 sc injections (1.5 mL each) at visit 2 (randomization), visit 3 (week 4), and visit 4 (week 8).

The randomization code will be generated by the interactive response technology (IRT) third-party vendor according to specifications from the Biostatistics Department. A Teva statistician will be responsible for reviewing the dummy randomization codes, and the final randomization code will be maintained by the third-party vendor in a secure location.

After all patients have completed visit 5 and an unblinding request from the Teva statistician has been received, the third-party vendor will provide the unblinded IMP assignments according to the processes defined in the relevant Standard Operating Procedure (SOP).

The sponsor, investigators, study staff (except for staff involved in bioanalytical analyses), and patients will be blinded to treatment assignment during the double-blind treatment period of the study.

### **2.3. Data Monitoring Committee**

Not applicable.

[REDACTED]

### **2.5. Sequence of Planned Analyses**

#### **2.5.1. Planned Interim Analyses**

There will be no interim analysis. However, a database lock from the double-blind period will occur following the completion of visit 5 by the last patient. Unblinding will occur after the database lock from the double-blind treatment period.

#### **2.5.2. Final Analyses and Reporting**

A database lock from the double-blind treatment period will occur following the completion of visit 5 by the last patient. Unblinding will occur after the database lock from the double-blind treatment period. This SAP will be finalized before the database lock.

All endpoints related to the double-blind treatment period will be analyzed, including data up to visit 5.

Data collected from open-label treatment period (visit 5 and after) will be analyzed separately after study completion.

### **3. ANALYSIS SETS**

#### **3.1. Intent-to-Treat Analysis Set**

The intent-to-treat (ITT) analysis set will include all randomized patients.

In the ITT analysis set, treatment will be assigned based on the treatment to which patients were randomized, regardless of which treatment they actually received.

#### **3.2. Open-Label Intend-to-Treat Analysis Set**

The open-label ITT (OL-ITT) analysis set is a subset of the ITT analysis set including only patients who receive at least 1 dose of study drug during the open-label treatment period.

Note, OL-ITT will be used for open-label analysis.

#### **3.3. Safety Analysis Set**

The safety analysis set will include all randomized patients who receive at least 1 dose of the IMP.

In the safety analysis set, treatment will be assigned based on the treatment patients actually received in the double-blind treatment period, regardless of the treatment to which they were randomized, unless otherwise specified.

Patients randomized to placebo group but received any number of injection of fremanezumab in error will be analyzed in a separated group (Other) in the safety analyses if applicable.

#### **3.4. Full Analysis Set**

The full analysis set (FAS) is a subset of the ITT analysis set including only patients who receive at least 1 dose of the IMP and have at least 1 post-baseline efficacy assessment on the primary endpoint.

In the FAS, treatment will be assigned based on the treatment to which patients were randomized, regardless of which treatment they actually received.

#### **3.5. Per-Protocol Analysis Set**

The per-protocol (PP) analysis set is a subset of the ITT analysis set including only patients without any major protocol deviations. Major protocol deviations will be determined before unblinding and database lock.

#### **3.6. Patients in Extension or Open-Label Period**

This will include patients continued in the extension or open-label period.

## **4. GENERAL ISSUES FOR DATA ANALYSIS**

### **4.1. General**

Descriptive statistics for continuous variables include count (n), mean, SD, standard error (SE), median, minimum, and maximum. In addition, for fremanezumab concentration, percentage coefficient of variation (%CV) and geometric mean will also be calculated. Descriptive statistics for categorical variables include patient counts and percentages, and a missing category will be displayed as appropriate.

Summaries of potentially clinically significant abnormal values for clinical laboratory tests and vital signs values will include all postbaseline values (including scheduled, unscheduled, and early withdrawal visits).

### **4.2. Specification of Baseline Values**

For analyses of the double-blinded treatment period, baseline is the last observed data before the administration of the first dose of the IMP, unless otherwise noted. For data collected in the e-diary daily, baseline will be derived from the baseline period (from the day of the informed consent to before the administration of the first dose of the IMP) and prorated to 28 days if the number of days in the baseline period is not equal to 28. Details are provided in Section 6.1.

For analyses of the open label treatment period, the baseline is the observed data at visit 5, unless otherwise noted.

### **4.3. Handling Withdrawals and Missing Data**

For efficacy analyses based on e-diary data, the missing data handling methods are provided in Section 6.1.4. For the efficacy analyses based on non-e-diary data, missing data handling methods, if applicable, will be provided in the efficacy analysis section for that endpoint.

Dates that have incomplete information (ie. only month and year or only year recorded) will be estimated for the purpose of calculating variables that are dependent on time if necessary. Day will be estimated as the first day (01) of the month (if month and year of partial date are available) or middle (July 1) of the year (if only year is available), unless otherwise noted. If no date information is recorded, the date will not be imputed.

The imputations for partial dates are only for calculation purpose. Original date variables will not be modified. Listings will present dates as collected. If no date information is recorded, the date will not be imputed.

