### **5.3. Demographics and Baseline Characteristics**

The demographic data will be collected at the screening visit after the patient signs the informed consent form. Patient demographic data including age, age group (<65 or ≥65 years old), gender, race, race group (white or other), ethnicity, baseline weight (kg), baseline height (cm), and baseline body mass index (kg/m^2) will be summarized using descriptive statistics for all analysis sets.

Baseline characteristics including time since the head trauma, duration of PTH history (less than 12 month since the brain injury versus greater or equal to 12 month since the brain injury), diagnosis of PTH, preventive medication use (yes or no) at screening or baseline, use of any acute headache medication (opioid, barbiturate, triptan, and NSAIDS) during the baseline period (yes or no), use of prescription abortive headache medication (opioid, barbiturate, and triptan) during the baseline period (yes or no), and monthly average number of headache days of at least moderate severity during the baseline period will be summarized for the ITT analysis set using descriptive statistics. No inferential analyses will be performed.

The time (in year) since the head trauma will be calculated as (the date of informed consent – the date of head trauma + 1)/365.25. Rules for handling partial head trauma date are in Section 4.3.

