### **8.3. Adverse Events**

Adverse events will be recorded from time informed consent is obtained through the end of study participation.

The following are considered protocol-defined adverse events of special interest (PDAESI) to be sent to the sponsor's Global Patient Safety and Pharmacovigilance Department for evaluation: ophthalmic-related adverse events of at least moderate severity, events of possible drug-induced liver injury (AST or ALT  $\geq 3 \times$  ULN, total bilirubin  $\geq 2 \times$  ULN, or international normalized ratio  $> 1.5$ ), Hy's Law events, or events of anaphylaxis and severe hypersensitivity.

All adverse events will be coded using MedDRA. Each patient will be counted only once in each preferred term or SOC category for the analyses of safety. Summaries will be presented for all adverse events (overall and by severity), adverse events determined by the investigator to be related to test IMP (defined as related or with missing relationship) (overall, overall by severity, serious AEs, PDAESI), serious adverse events, PDAESI, and adverse events causing withdrawal from the study. Adverse events with the missing flag indicating serious will be excluded from the summary of serious adverse events but included in the summary of non-serious adverse events.

Summaries for injection site adverse events will be presented (overall and by severity).

Listings for deaths, serious adverse events, adverse events leading to treatment withdrawn, adverse events leading to study discontinuation, adverse event requiring concomitant or additional treatment, injection site adverse events, PDAESI, and hypersensitivity and suspected anaphylaxis/hypersensitivity reactions related adverse events will be presented. In addition, listings for MedDRA dictionary terms for adverse event descriptions and adverse event preferred terms by patient number and treatment group will be presented.

Spontaneous abortion or an elective abortion due to developmental anomalies will be reported as a serious adverse event (protocol Section 7.2). These serious adverse events will be listed separately if applicable.

Summaries will include treatment-emergent adverse events which are defined as adverse events occurring at or after the first dose of the IMP. The listing will include all adverse events recorded.

Adverse events for patients who did not meet screening criteria will be listed.

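### Setting a missing onset day to the 1st of the month dates some post-dose adverse events before dose 1 and removes them from the treatment-emergent summaries

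*SAP*

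**What the plan says.** SAP 4.3 (Handling Withdrawals and Missing Data) says that incomplete dates "will be estimated for the purpose of calculating variables that are dependent on time if necessary". With month and year known, "Day will be estimated as the first day (01) of the month (if month and year of partial date are available"; with only the year known, the date goes to the "or middle (July 1) of the year (if only year is available), unless otherwise noted". A wholly missing date is not imputed. The original variables are unchanged, and listings show dates as collected.

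SAP 8.3 (Adverse Events) says: "Adverse events will be recorded from time informed consent is obtained through the end of study participation". The recorded events can therefore include some from before dosing, and the onset date separates the two kinds. On content it says: "Summaries will include treatment-emergent adverse events which are defined as adverse events occurring at or after the first dose of the IMP". It adds: "The listing will include all adverse events recorded". It has no rule for partial onset dates, and none appears elsewhere in the available SAP or protocol text.

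The one variable that refers to the date rule by section is the head trauma date, in SAP 5.3: "Rules for handling partial head trauma date are in Section 4.3".

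**The concern.** Treatment-emergent status depends on comparing onset with dose 1, so it is a time-dependent variable. With nothing noted otherwise, the general rule in SAP 4.3 governs it. Moving a missing day to the 1st can only shift onset earlier. At the dose 1 boundary the rule can therefore only take true post-dose events out of the summaries; it can never add one wrongly. The loss falls on the weeks after the first injection, when early reactions are of most interest. With recruitment stopped at 87 patients, one event can change a table row.

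SAP 8.3 is cautious about another gap in the data: an event with missing relationship is counted as related. An incomplete or missing onset date has no such protection.

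Two further uses of the rule raise similar questions. SAP 8.1 reports safety up to visit 5 separately from the open-label period, so a shifted date can put an event in the wrong period. A year-only head trauma date can be placed after consent.

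**Working it through.** The plan states no figure to reproduce. The check is date logic, followed by enumeration under stated assumptions.

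**Inputs**
- Missing day becomes the 1st; year only becomes 1 July (SAP 4.3).
- Treatment-emergent means onset at or after dose 1 (SAP 8.3).
- Double-blind period of 84 days (visit 2 at day 0 to visit 5 at day 84, SAP Table 1).
- Assumed: dose 1 uniform over 1 November 2017 to 30 March 2020 (881 dates), and true onset uniform over the first 28 or 84 days.
- Assumed: 1%, 5% or 10% of events lack the onset day. The documents give no figure.

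**Example.** Dose 1 is on 14 May 2019 and onset is recorded as May 2019. The imputed onset is 1 May, 13 days before dose 1, so the event is not treatment-emergent.

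**How often the boundary is crossed.** The 1st precedes dose 1 unless dose 1 is itself on the 1st. That holds for (881 − 29)/881 = 96.7% of the assumed dose dates.

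**Share of missing-day events lost.** If dose 1 is on day *d* of a month with *m* days, post-dose onsets on the remaining *m − d + 1* days of that month are lost when *d* > 1. Onsets in later months are safe.
- 84-day period, 30-day month: (29 + 28 + … + 1)/(30 × 84) = 435/2,520 = 17.3%. For a 31-day month: 465/2,604 = 17.9%. Enumeration over all 881 dates: 12,981/74,004 = 17.5%.
- First 28 days, 30-day month: (28 + 28 + 27 + … + 1)/(30 × 28) = 434/840 = 51.7%. Enumeration: 12,921/24,668 = 52.4%.

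**Share of all double-blind treatment-emergent events lost** = (share lacking the day) × 0.175:

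| Share lacking the day | Loss |
|---|---|
| 1% | 0.2% |
| 5% | 0.9% |
| 10% | 1.8% |

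**Year-only onsets.** Under the same assumptions, 1 July falls before dose 1 for about 35% of true events in the 84 days. This figure depends on the assumed calendar of dosing.

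**Visit 5.** The missing-day rule moves 0% of double-blind events into the open-label period, because it never moves a date later. In the other direction, 17.5% of missing-day events from the 84 days starting at visit 5 are dated before visit 5. For a patient randomized to placebo, an event on open-label fremanezumab could then be counted under placebo. Only a year-only date can move a double-blind event past visit 5.

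**Head trauma.** SAP 5.3 computes (consent date − trauma date + 1)/365.25. With consent on 15 March 2019 and trauma recorded as 2019, the imputed trauma date is 1 July 2019 and the result is (−108 + 1)/365.25 = −0.29 years.

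**The case against.** The strongest reply is that the use of SAP 4.3 for adverse event onset is inferred, since only the head trauma date refers to that section. This is a fair caution. But the rule is worded for any time-dependent variable unless noted otherwise, and SAP 8.3 notes nothing.

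The second reply is that partial onset dates should be rare. Protocol 7.1.2 requires onset and end dates on source and CRF, Table 1 asks about adverse events before and after dosing at visits 2 to 7, and Appendix P has missing data queried. Injection sites are assessed immediately and at 1 hour, so reactions seen then have a known date. Protocol 7.1.1 also sends occurrences before dose 1 to medical history. All of this stands and keeps the effect small. The last item cuts both ways, however. If sites followed it, every event on the adverse event page is post-dose, and an imputed pre-dose date is always wrong. It also conflicts with recording from consent in Protocol 7.1.2 and SAP 8.3; those passages need reconciling.

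Three stronger readings are tempting, and the documents do not support them:
- *Every event in the first-dose month is lost.* Only those with an incomplete onset date are affected.
- *Events vanish from the report.* SAP 8.3 keeps all recorded events in the listing and has separate listings for deaths, serious events and events of special interest.
- *The missing-day rule pushes double-blind events into the open-label period.* It moves dates only earlier, so the error at visit 5 runs the other way.

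**Conclusion.** The point holds for adverse events with a partial onset date. As written, the SAP classes a missing-day event in the month of dose 1 as pre-dose for nearly every possible dose date and drops it from the treatment-emergent summaries. This is a stated default giving a wrong result in the anti-conservative direction, not just a missing detail.

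The 18% and 52% are shares of missing-day events, not of all events. A reader might take them as the overall loss, but that would require every event to lack its onset day. The overall loss is about 0.2% to 1.8% of double-blind treatment-emergent events under the assumed 1% to 10%, which could be no events at all in a trial of 87 patients. The figures rest on uniform onset and uniform dose dates.

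The visit 5 misallocation and the negative time since trauma are real but secondary. The trauma case needs a year-only date in the consent year with consent before 1 July, and SAP 5.3 uses the variable descriptively only. Efficacy conclusions are not affected.

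**What to change.** Add a short paragraph to SAP 4.3 and 8.3:

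1. **Dose 1.** If a partial onset date is compatible with the month (or, for year only, the year) of dose 1, and the end date does not show that the event ended before dose 1, set onset to the dose 1 date. Count events with undeterminable onset as treatment-emergent. No true treatment-emergent event is then lost through imputation at dose 1.
2. **Visit 5.** State a separate rule, fixed before unblinding. Do not copy the dose 1 logic: it would move ambiguous events in the visit 5 month into the open-label period and out of the randomized comparison.
3. **Head trauma.** Constrain the imputed date to agree with the entry criterion of headache for more than 1 month after injury (Protocol 4.1). Capping it at the consent date is not enough, because that gives 1/365.25 of a year since trauma.

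The cost is one paragraph and a small programming change. The downside is that a few pre-dose events may be counted as treatment-emergent, which is the conservative direction for safety. If the double-blind data have already been unblinded, report the dose 1 rule as an added analysis and disclose it in the clinical study report, as Protocol Section 9 provides for later changes.

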### **4.4. Study Days and Visits**

For by-visit summaries, if there are multiple assessments at a postbaseline visit then the last non-missing assessment at that visit will be used for the summary (this includes scheduled and unscheduled assessments), except for triplicate ECG assessments (see Section 8.11 for further details).

Study visits are detailed in [Table 1](#).

**Table 1: Study Visits**

Visit #	V1 (Screening)	Double-Blinded Treatment Period			Open-Label Period			
		V2 	V3	V4	V5 	V6	V7	V8
Day	-28 to-1	0±3	28±3	56±3	84±3	112±3	140±3	168±3
Week	-	0	4	8	12	16	20	24
	Visit 1	Visit 2 Dose 1	Visit 3/ Dose 2	Visit 4/ Dose 3	Visit 5/ Dose 4/ EODBT	Visit 6/ Dose 5	Visit 7/ Dose 6	Visit 8/ EOT/EOS/ET 

 Baseline/Randomization

 Visit 5 is the end of double-blind treatment period and the beginning of open-label period

 EOT=the end of treatment; EOS=end of study; ET=early termination

The end of double-blind treatment period (EODBT) is defined as Visit 5/Week 12 or early termination (ET) visit for patients did not complete double-blind treatment period and did not continue in open-label period.

‘Last Assessment’ may be derived for analysis purpose for safety data and is defined as the last observed postbaseline data during the double-blind treatment period for double-blind period or the last observed postbaseline data during the open-label treatment period for open-label period.

For patients who withdraw from the study early, their data at the early withdrawal visit will be excluded from the by-visit summaries but will be included in the ‘Last Assessment’ summaries.

Study days are numbered relative to the first day of the IMP administration. The start of treatment (day 1) is defined as the date on which a patient takes the first dose of the IMP, as recorded on the case report form (CRF). Days will be numbered relative to treatment start (ie, ..., -2, -1, 1, 2, ...; with day 1 being the day of the first IMP administration and day -1 being the day before the day of the first IMP administration).

For data from the e-diary, monthly analysis windows [Month 1 (weeks 1 to 4), Month 2 (weeks 5 to 8), and Month 3 (weeks 9 to 12)] will be derived for the purpose of efficacy endpoint analyses. Details are provided in Section 6.1.3.

